6.4.2 Definitions of serious adverse event

A serious adverse event is an AE occurring during any study phase (ie, run-in, treatment, washout, follow-up), that fulfils one or more of the following criteria:

- Results in death
- Is immediately life-threatening
- Requires in-patient hospitalisation or prolongation of existing hospitalisation

Japan specific definition:

Requires in-patient hospitalisation or prolongation of existing hospitalisation (including hospitalisation for tests related to adverse events), except hospitalisation that has been planned before enrolment

- Results in persistent or significant disability or incapacity
- Is a congenital abnormality or birth defect
- Is an important medical event that may jeopardise the subject or may require medical intervention to prevent one of the outcomes listed above.

The causality of SAEs (ie, their relationship to study treatment) will be assessed by the investigator(s), who in completing the relevant eCRF must answer “yes” or “no” to the question “Do you consider that there is a reasonable possibility that the event may have been caused by any of the following – study medication – other medication?”. For further guidance on the definition of a SAE and a guide to the interpretation of the causality question, see Appendix B to the Clinical Study Protocol.

Note that SAEs that could be associated with any study procedure should also be reported. For such events the causal relationship is implied as “yes”. Elective hospitalisations to facilitate treatment procedures should not be reported as SAEs.

6.4.3 Recording of adverse events

Time period for collection of adverse events

Non serious AEs and SAEs will be collected from the time of patient informed until 4 weeks after the final administration of ZOLADEX 3.6 mg or 12 weeks after the final administration of ZOLADEX 10.8 mg (see Section 3.1).

Follow-up of unresolved adverse events

After the initial AE/SAE report the investigator(s) is required to follow up proactively each patient and provide further information to the sponsor on the patient's condition. During the study all AE/SAEs should be followed up to resolution or until the condition stabilises, unless the event is considered by the investigator(s) to be unlikely to resolve due to the patient's underlying disease (in these cases, the investigator(s) must record their opinions in the patient's medical records), or the patient is lost to follow-up.

AstraZeneca reserves the right to ask for further information on any AE which may be considered of interest.

Variables

The following variables will be collect for each AE;

- AE (verbatim)
- Date when the AE started and stopped
- Maximum CTCAE grade (For CTCAE version 3.0, see Appendix F)
- Whether the AE is serious or not
- Investigator causality rating against the each Investigational Product (yes or no) : ZOLADEX 3.6 mg, ZOLADEX 10.8 mg and tamoxifen
- Causality assessment in relation to Other medication
- Action taken with regard to investigational product
- Subject received any treatments (yes or no)
- Outcome.

In addition, the following variables will be collected for SAEs:

- Date AE met criteria for serious AE
- Date Investigator became aware of serious AE

- AE is serious due to
- Date of hospitalisation
- Date of discharge
- Probable cause of death
- Date of death
- Autopsy performed
- Causality assessment in relation to Study procedure(s)
- Description of AE

It is important to distinguish between serious and severe AEs. Severity is a measure of intensity whereas seriousness is defined by the criteria in Section 6.4.2. An AE of severe intensity need not necessarily be considered serious. For example, nausea that persists for several hours may be considered severe nausea, but not a SAE. On the other hand, a stroke that results in only a limited degree of disability may be considered a mild stroke but would be a SAE.

Causality collection

The Investigator will assess causal relationship between Investigational Product and each Adverse Event, and answer “yes” or “no” to the question “Do you consider that there is a reasonable possibility that the event may have been caused by the investigational product?”

For SAEs causal relationship will also be assessed for other medication and study procedures and additional study drug. Note that for SAEs that could be associated with any study procedure the causal relationship is implied as “yes”.

A guide to the interpretation of the causality question is found in Appendix B to the Clinical Study Protocol.

Adverse Events based on signs and symptoms

All AEs spontaneously reported by the subject or reported in response to the open question from the study personnel: “*Have you had any health problems since the previous visit/you were last asked?*”, or revealed by observation will be collected and recorded in the eCRF. When collecting AEs, the recording of diagnoses is preferred (when possible) to recording a list of signs and symptoms. However, if a diagnosis is known and there are other signs or symptoms that are not generally part of the diagnosis, the diagnosis and each sign or symptom will be recorded separately.

Adverse Events based on examinations and tests

The results from protocol mandated laboratory tests and vital signs will be summarised in the clinical study report. Deterioration as compared to baseline in protocol-mandated laboratory values should therefore only be reported as AEs if they fulfil any of the SAE criteria or are the reason for discontinuation of treatment with the investigational product.

If deterioration in a laboratory value/vital sign is associated with clinical signs and symptoms, the sign or symptom will be reported as an AE and the associated laboratory result/vital sign will be considered as additional information. Wherever possible the reporting investigator(s) uses the clinical, rather than the laboratory term (eg, anaemia versus low haemoglobin value). In the absence of clinical signs or symptoms, clinically relevant deteriorations in non-mandated parameters should be reported as AE(s).

Deterioration of a laboratory value, which is unequivocally due to disease progression, should not be reported as an AE/SAE.

Any new or aggravated clinically relevant abnormal medical finding at a physical examination as compared with the baseline assessment will be reported as an AE.

Disease progression

Disease progression can be considered as a worsening of a subject's condition attributable to the disease for which the investigational product is being studied. It may be an increase in the severity of the disease under study and/or increases in the symptoms of the disease. Events, which are unequivocally due to disease progression, should not be reported as an AE during the study.

Recurrence

Any events that are unequivocally due to recurrence of the breast cancer must not be reported as an AE (see Section 6.4.1).

Deaths

All deaths that occur during the study, or within the protocol-defined follow-up period after the administration of the last dose of study treatment, must be reported as follows:

- Death that is clearly the result of disease progression should be reported to the study monitor at the next monitoring visit and should be documented in the eCRF but should not be reported as a SAE
- Where death is not due (or not clearly due) to progression of disease under study, the AE causing the death must be reported to the study monitor as a SAE within 24 hours. The report should contain a comment regarding the co-involvement of progression of disease, if appropriate, and should assign main and contributory causes of death

- Deaths with an unknown cause should always be reported as a SAE. A post mortem may be helpful in the assessment of the cause of death, and if performed a copy of the post mortem results should be forwarded to the sponsor within the usual timeframes

A statement of death form should be submitted at any point during the study (to the sponsor) when a patient has died.

New cancers

The development of a new cancer should be regarded as an AE and will generally meet at least one of the seriousness criteria. New cancers are those that are not the primary reason for the administration of the study treatment and have been identified after the inclusion of the patient into the study. They do not include metastases of the original cancer. Symptoms of metastasis or the metastasis itself should not be reported as an AE/SAE as they are considered to be disease progression.

Overdose

Should an overdose (accidental or deliberate) occur, it must be reported in accordance with the procedures described in Section 13.2 regardless of whether the overdose was associated with any symptom or not. All symptoms associated with the overdose should be reported as AEs.

Pregnancy

Should a pregnancy occur, it must be reported in accordance with the procedures described in Section 13.3. Pregnancy in itself is not regarded as an AE unless there is a suspicion that an investigational product may have interfered with the effectiveness of a contraceptive medication.

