Final assessment of safety will be done at Week 24 (Study completion visit) but if criterion for treatment discontinuation is met before Week 24, the assessment will be done 12 weeks after the final administration of ZOLADEX 10.8 mg or 4 weeks after the final administration of ZOLADEX 3.6 mg respectively or at Week 24 whichever is sooner.

The principal investigator/sub-investigator is responsible for following the schedule of study procedures as defined in the study protocol.

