3.1.1 PK subgroup and schedule

Additional blood samples will be collected from at least 20 evaluable patients (PK subgroup) randomised to ZOLADEX 10.8 mg for assessment of goserelin plasma concentrations. Additional E₂ serum concentration assessments will also be made in these patients.

At least 10 Japanese patients will be recruited from Japan and at least 10 Non Japanese patients will be recruited from non-Japanese countries except for China.

Patients will attend all main study visits (see Table 2) and will have additional visits for collection of blood samples at the schedule shown in Table 1.

[figure not shown]
Table 1 Study schedule for pharmacokinetic subgroup

Blood sample for:	Time point for sampling							
	Day 1	Day 1	Day 1	Day 2	Day 3	Wk 4	Wk 12 ^b	Wk 24
	Pre-dose	1 h ±5 mi n	2 h ±5 mi n	24 h ±2 h	48 h ±2 h	±7d	±7d ^b	±7d
Goserelin plasma conc.	X	X	X	X	X	X	X	X
E ₂ serum conc. ^a		X	X	X	X	X		

a) Only samples in addition to those scheduled for the main study (see Table 2) are included.

b) The sample should be taken prior to ZOLADEX 10.8 mg administration.

Figure 1 Study flow chart

a) Make sure that interval of the administration should not meet the criteria of Overdose (see Section 13.2)

- j) Zoladex 3.6 mg will be administered every 4 weeks from Day 1 until Week 20. Zoladex 10.8 mg will be administered at Day 1 and Week 12.
- k) Any patient who discontinues treatment for reasons other than disease progression (except for withdrawal of consent) should continue, where possible, to have objective tumour assessments until week 24 or until objective progression is confirmed according to RECIST (Ver1.1) which is sooner.

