5. STUDY CONDUCT

5.1 Restrictions during the study

1. anti-coagulant therapy
 - Patients receiving long-term anti-coagulant therapy with warfarin should be managed appropriately to reduce the risk of injection site reactions
 - Patients who need to begin anti-coagulant therapy while receiving study treatment may be treated at the discretion of the investigator(s). There is an

increased risk of haemorrhage in these patients and the investigator(s) should decide whether that risk is outweighed by the possible benefits of continued treatment

2. anti-platelet therapy (eg, acetylsalicylic acid, ticlopidine, clopidogrel)
 - Patients receiving anti-platelet may be at increased risk of bleeding from injection. The investigator(s) should decide whether the risk is outweighed by the possible benefits of continued treatment. It is advised to apply direct pressure to the injection site in these patients
3. Medication including over-the-counter medications which are known to affect sex hormone status (eg, hormone replacement therapy [HRT] or oral contraceptives)
 - They are not permitted since informed consent until final administration of study medication including study concomitant medication.
4. Anti-cancer chemotherapy, radiotherapy or trastuzumab or lapatinib
 - They must not be started after from entry to the study through to final administration of study medication including study concomitant medication; if needed due to disease progression (as confirmed by imaging) the patient should be withdrawn from the study
5. Contraception
 - Non-hormonal methods of contraception should be used from signing informed consent until study completion visit
6. Blood donation
 - Blood donation should be restricted since informed consent until study completion visit

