5.6.3 Medication after discontinuation of study drug

Medication after discontinuation of study drug is at the discretion of the investigator(s).

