12.2.2 Analysis of safety outcome variables (main study)

12.2.2.1 Adverse events

AEs will be classified by MedDRA preferred term (PT) and system organ class (SOC).

All data on AEs that occurred after obtaining informed consent will be listed. AEs that occurred after administration of the investigational product will be summarised by treatment group, SOC, PT and the worst Grade of CTCAE v3.0. Drug related adverse events data will also be summarised in the same manner.

Individual patient data on all SAEs, deaths and AEs leading to discontinuation of the study as well as all AEs assessed, as OAEs will be listed.

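### For patients who stop between injections, AE collection lasts longer on 10.8 mg than on 3.6 mg, and the all-cause AE summary makes no cut at later anticancer therapy

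*Protocol*

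**What the plan says.** Section 2.2 makes the comparison of safety and tolerability between the two depots, through AEs, a secondary objective.

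- **Collection.** Section 6.4.3 collects AEs from consent "until 4 weeks after the final administration of ZOLADEX 3.6 mg or 12 weeks after the final administration of ZOLADEX 10.8 mg" and refers to Section 3.1. For patients who meet a discontinuation criterion before Week 24, Section 3.1 places the final safety assessment "12 weeks after the final administration of ZOLADEX 10.8 mg or 4 weeks after the final administration of ZOLADEX 3.6 mg", but adds "or at Week 24 whichever is sooner".
- **Dosing.** Section 3.1.1 gives the injection times: "Zoladex 10.8 mg will be administered at Day 1 and Week 12"; "Zoladex 3.6 mg will be administered every 4 weeks from Day 1 until Week 20".
- **Other therapy.** On chemotherapy, radiotherapy, trastuzumab and lapatinib, Section 5.1 (item 4) says: "They must not be started after from entry to the study through to final administration of study medication including study concomitant medication". The same item says that a patient who needs such therapy for imaging-confirmed progression is to leave the study. Section 5.6.3 leaves medication after study drug to the investigator's judgement.
- **Analysis.** Section 12.2.2.1: "AEs that occurred after administration of the investigational product will be summarised by treatment group, SOC, PT and the worst Grade of CTCAE v3.0". It sets no end point and no cut at later therapy. Drug-related AEs are tabulated in the same way.

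**The concern.** For a patient who stops early, the length of AE collection depends on the assigned depot. Progression is itself a reason to stop (Section 5.8), so other anticancer therapy inside the collection window is foreseeable. An AE on that therapy enters the by-arm table under the assigned depot, and the 10.8 mg arm has more weeks in which this can happen.

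The crude all-cause incidence and the worst-grade summary would then compare the arms over unequal follow-up. The direction is against 10.8 mg. The comparison that Section 2.2 asks for would partly reflect how long patients were watched and what they received next.

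**Working it through.** **The plan's own figure.** The protocol gives no number on this point. Its one design calculation reproduces: 2 × 0.7 × 0.3 × 7.849 / 0.175² = 107.6, so 108 per arm and 216 in total (7.849 is the squared sum of the normal quantiles for one-sided 2.5% and 80% power). The point does not depend on it.

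**Inputs.** Injections at Weeks 0 and 12 (10.8 mg) and at Weeks 0, 4, 8, 12, 16 and 20 (3.6 mg), from Section 3.1.1. Windows of 12 and 4 weeks after the last injection, from Sections 3.1 and 6.4.3. Week 24 limit from Section 3.1. Assumption: stopping times uniform over 24 weeks.

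**Completers.** 12 + 12 = 24 and 20 + 4 = 24. Both arms are followed to Week 24.

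**Early stoppers.** Weeks of collection left = min(last injection + 12 or + 4, 24) − stopping week.

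| Stop at week | 10.8 mg | 3.6 mg |
|---|---|---|
| 2 or 14 | 10 | 2 |
| 6 or 18 | 6 | 2 |
| 10 or 22 | 2 | 2 |
| 12, before that day's injection | 0 | 0 |
| 12, just after it | 12 | 4 |

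The excess is 8, 4 or 0 weeks in the first, middle and last third of each 12-week interval.

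**Mean under uniform stopping.** 12/2 = 6.0 weeks and 4/2 = 2.0 weeks. The 10.8 mg share of post-stop time is 6/(6 + 2) = 75%.

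**Delay L before later therapy starts.** Mean exposed time is (12 − L)²/24 on 10.8 mg and (4 − L)²/8 on 3.6 mg.
- L = 1: 5.04 v 1.13 weeks, share 82%.
- L = 2: 4.17 v 0.50 weeks, share 89%.
- L = 4: 2.67 v 0 weeks, share 100%.

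**Chance that an early stopper has a later-therapy AE recorded.** Assume that therapy starts at once and that AEs occur at rate r per week. The chance is 1 − (1 − e^(−wr))/(wr), with w = 12 or 4.
- r = 0.05: 25% v 9%.
- r = 0.10: 42% v 18%.
- r = 0.25: 68% v 37%.

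**Whole-arm effect.** Let a fraction f of each arm stop early, at Week 12 on average. Per patient, the 3.6 mg arm has 24(1 − f) + 12f + 2f = 24 − 10f weeks, and the 10.8 mg arm has 4f more.
- f = 5%: 0.2/23.5 = 0.9% more.
- f = 15%: 0.6/22.5 = 2.7% more.
- f = 30%: 1.2/21 = 5.7% more.
- Taken as a share of the 10.8 mg arm's own time (24 − 6f), the range is 0.2/23.7 = 0.8% to 1.2/22.2 = 5.4%.
- If half of the stops fall at Week 12 before dosing, the excess is 2f/(24 − 11f), or 0.4% to 2.9%.

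**Would a limit of 4 weeks after discontinuation equalise the arms?** No. On 3.6 mg, collection already ends 2.0 weeks after stopping on average. On 10.8 mg the mean of min(R, 4), with R uniform on 0 to 12, is 16/24 + 4 × 8/12 = 3.3 weeks.

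**Passages side by side.** Section 3.1 stops at Week 24 at the latest. Section 6.4.3 states no such limit, though it refers to Section 3.1. With the ±7-day dosing window in Section 5.5.2.1, a last injection one week late takes the Section 6.4.3 window to 13 + 12 = 25 or 21 + 4 = 25 weeks. Section 5.1 has patients who need other therapy for progression leave the study, while Section 3.1 continues safety assessment after treatment stops. Section 5.9 describes withdrawal (of consent) as from product and assessments, yet has AEs followed up.

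**The case against.** The strongest reply is that this is an analysis detail for the SAP, to which Section 12 defers fuller specification, and that nothing in Section 12.2.2.1 forbids a cut. That lowers the weight of the point but does not remove it. The unequal windows and the count of all post-dose AEs by arm are stated rules, and following them as written produces the imbalance.

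Second, each window equals one depot interval, which is a visible reason for its length. That supports collecting the data, and collection need not change. It does not support comparing crude counts over unequal follow-up.

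Third, there are safeguards. AE dates are recorded, and Section 6.4.3 lists causality to other medication. Drug-related AEs are tabulated separately, events unequivocally due to progression are not AEs, and Section 12.2 confines formal testing to efficacy and PD. The drug-related tables are therefore less affected. The protection is partial: the study is open label, the causality paragraph in Section 6.4.3 describes attribution to other medication only for SAEs, and the all-cause table is not protected.

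Fourth, uniform stopping may not fit the schedule. Progression is assessed at Weeks 12 and 24 and otherwise as clinically indicated (Section 3.1). Stops at Week 12 before dosing, or at Week 24, create no imbalance. This stands and reduces the size.

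Fifth, if the Section 5.1 clause ends all assessment when therapy for progression is needed, collection might not run on into that therapy. Section 3.1 points the other way, so the text is unclear rather than reassuring.

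**Conclusion.** The point holds in limited form. For patients who stop between injections, the all-cause AE comparison includes more post-stop time, and more scope for later-therapy events, in the 10.8 mg arm: a mean of 6 v 2 weeks under uniform stopping, which is an assumption. Completers and stops at Week 12 before dosing are unaffected. Overall the 10.8 mg arm has about 0.9% to 5.7% more collection time than the 3.6 mg arm if 5% to 30% stop early. That range is also assumed. Section 12.3 expects about 30% not progression-free at Week 24, but progressions first found at Week 24 do not count here.

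A reader might infer more than the protocol supports:
- That later-therapy events on 10.8 mg have no counterpart on 3.6 mg. They do, since that arm also has post-stop collection, 2 weeks on average.
- That every early stopper on 10.8 mg adds 8 weeks. That is the maximum; the mean excess is 4 weeks under uniform stopping.
- That the bias falls on severe and serious events. This is plausible if later therapy is chemotherapy, but nothing in the protocol quantifies it.
- That harm from 10.8 mg could be hidden. The direction is the opposite.

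The body of Table 2 and any SAP were not available; either could narrow the point.

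**What to change.** Keep AE collection and the all-AE table as they are. In Section 12.2.2.1, add a between-arm AE summary that:
- excludes events starting after the first other anticancer therapy;
- is capped at Week 24;
- reports events per person-time at risk, to handle the follow-up difference that remains where no new therapy starts.

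List the later events separately. Do not present a limit of 4 weeks after discontinuation as a common window, since it leaves 3.3 v 2.0 weeks.

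Reconcile Sections 3.1 and 6.4.3 on the Week 24 limit. Reconcile the study-withdrawal clause in Section 5.1 with the continued safety assessment in Section 3.1.

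The cost is wording and one extra table. AE dates (Section 6.4.3) and concomitant medications up to the study completion visit (Section 6.2.1) are already collected; the sponsor should confirm that start dates of radiotherapy are captured too. The downside is that some genuine late 10.8 mg events fall outside this summary, which is why the all-AE table stays beside it.

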3.1 Overall study design and flow chart

This is a multicentre, open label, randomised, parallel group study to compare ZOLADEX 10.8 mg given every 12 weeks with ZOLADEX 3.6 mg given every 4 weeks.

Target subject population

Pre-menopausal female patients with locally advanced or metastatic ER positive breast cancer. (See Section 4.1 and 4.2 for inclusion and exclusion criteria)

Study medication

‘Study medication’ is a combination of investigational product ‘ZOLADEX 10.8 mg’ or comparator ‘ZOLADEX 3.6 mg’ and study concomitant medication ‘tamoxifen’.

Study period

This study period is composed of screening period and study treatment /assessment period.

Screening period (Visit 1, Day – 21 to Day 0)

- Only eligible patients should be randomised by assessment based on the inclusion criteria and exclusion criteria (See Section 4.1 and 4.2).

- Eligible patients will be randomised 1:1 to receive ZOLADEX 10.8 mg or ZOLADEX 3.6 mg at visit 2.

Treatment/Assessment period

Administration of Investigational product (ZOLADEX 10.8 mg) or comparator (ZOLADEX 3.6 mg) should be started within 1 day after randomisation. Study concomitant medication (Tamoxifen 20 mg) should be started on the same day of or one day after starting the administration of ZOLADEX.

Study medication will be administered from Day 1 until completion of 24 weeks of study treatment or any other criterion for treatment discontinuation are met whichever is sooner. In other words, administration of ZOLADEX 10.8 mg will be continued until Week 12 or any other criterion for treatment discontinuation are met whichever is sooner. Administration of ZOLADEX 3.6 mg will be continued until Week 20 or any other criterion for treatment discontinuation are met whichever is sooner. Administration of tamoxifen will be continued until Week 24 or any other criterion for treatment discontinuation are met whichever is sooner.

Assessment schedule

Study visits to assess efficacy and safety are scheduled at Day 1 (Visit 2), Week 12 (Visit 3), and Week 24 (see Table 2 for study visit windows).

Assessments to identify disease progression will be conducted at each scheduled visit, Week 12 and Week 24. Assessments for progressive disease will also be done between scheduled visits as clinically indicated.

Final assessment of efficacy will be done at the time of disease progression or at Week 24 (Study completion visit) whichever is sooner.

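### The adverse-event collection window is timed from the last ZOLADEX injection only, so an early last injection closes it before tamoxifen and the Week 24 safety assessment end

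*Protocol*

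**What the plan says.** Section 6.4.3 runs AE and SAE collection from consent "until 4 weeks after the final administration of ZOLADEX 3.6 mg or 12 weeks after the final administration of ZOLADEX 10.8 mg", with a cross-reference to Section 3.1. The same section asks for a causality rating against tamoxifen as well as against each ZOLADEX strength.

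Section 3.1 defines study medication as ZOLADEX together with tamoxifen. On tamoxifen it says: "Administration of tamoxifen will be continued until Week 24 or any other criterion for treatment discontinuation are met whichever is sooner". On the end of safety follow-up it says: "Final assessment of safety will be done at Week 24 (Study completion visit"), with a separate rule for early discontinuation: "if criterion for treatment discontinuation is met before Week 24, the assessment will be done 12 weeks after the final administration of ZOLADEX 10.8 mg". In the 3.6 mg arm the matching interval is 4 weeks, and in either arm Week 24 applies instead if it comes first. That rule, too, is timed from ZOLADEX alone.

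Other sections use a fuller end point. Section 5.1, on drugs that affect sex hormones, says: "They are not permitted since informed consent until final administration of study medication including study concomitant medication". The Deaths paragraph of 6.4.3 covers deaths during the study or "within the protocol-defined follow-up period after the administration of the last dose of study treatment".

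**The concern.** One of the two study drugs plays no part in deciding when AE collection stops. If the last injection is early, a patient who has followed the protocol in every respect can still be taking tamoxifen after the stated period has closed, with the final safety assessment still to come. Sections 6.4.3 and 3.1 then imply different end dates, and nothing says which governs.

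The safety objective compares two regimens that both contain tamoxifen. Section 13.2 lists hot flushes, vaginal bleeding, vaginal discharge, pruritus vulvae and tumour flare among its side effects. Many such events would be non-serious, and non-serious AEs have no second reporting rule to catch them. Sites and countries could settle the conflict differently.

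**Working it through.** **Inputs**
- Last planned injections (Section 3.1): "Administration of ZOLADEX 3.6 mg will be continued until Week 20" and "administration of ZOLADEX 10.8 mg will be continued until Week 12".
- Interval after the last injection (6.4.3): 4 weeks for 3.6 mg, 12 weeks for 10.8 mg.
- Injection window (5.5.2.1): ±7 days, read as applying to the scheduled weeks listed there.
- End of tamoxifen and final safety assessment (3.1): Week 24 = day 168.

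**Formulas.** Close = scheduled day of last injection + shift + interval after injection. Gap = 168 − close.

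**Planned schedule (shift 0).** This reproduces the protocol's own Week 24.
- 3.6 mg: 140 + 0 + 28 = day 168, gap 0.
- 10.8 mg: 84 + 0 + 84 = day 168, gap 0.

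**Last injection 7 days early.**
- 3.6 mg: 140 − 7 + 28 = day 161 (Week 23), gap 7 days.
- 10.8 mg: 84 − 7 + 84 = day 161 (Week 23), gap 7 days.

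**Last injection 7 days late.** Both arms close on day 175 (Week 25), so there is no gap.

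In both arms the period therefore closes at Week 24 plus the shift. The gap equals the number of days by which the last injection was early: at most 7 of 168 days (7/168 = 4.2%), and the same function of the shift in each arm.

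**Late completion visit.** Section 12.2.1.1 allows Visit 4 up to 7 days after Week 24. After an injection 7 days early, a Week 25 visit falls 175 − 161 = 14 days after the close. Tamoxifen exposure is uncovered for 14 days only if one assumes it is taken up to that visit. Section 3.1 ends it at Week 24.

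**Illustration of the average (assumption).** The protocol gives no distribution of injection dates. With a shift uniform on −7 to +7 days, the chance of an early last injection is 0.5 and the mean gap is (1/14) × (7²/2) = 49/28 = 1.75 days, or 1.75/168 = 1.0% of the treatment period. The range is 0 days (no early last injections) to 7 days (all at the early limit).

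**Missed last injection with tamoxifen continued (assumption).**
- 3.6 mg: last injection Week 16, close at Week 16 + 4 = Week 20, uncovered 24 − 20 = 4 weeks.
- 10.8 mg: last injection Day 1, close at Week 12, uncovered 24 − 12 = 12 weeks.

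**The case against.** The strongest defence is that the sections should be read together. Section 6.4.3 points to 3.1, which puts the final safety assessment at Week 24 for anyone who has not discontinued. The open AE question in 6.4.3 asks about problems since the last contact and says the answers are recorded. Section 6.4.4 requires reporting of every SAE in the course of the study, and the Deaths paragraph covers all deaths during it. Much of this stands: a sensible site would probably collect to Week 24, and SAEs and deaths are partly protected. But the collection sentence in 6.4.3 names SAEs as well as non-serious AEs, and the cross-reference leads to a different end date without saying which applies.

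It is also fair that injections at the early limit may be uncommon. That limit coincides with the interval in the overdose definition of Section 13.2, and a flow-chart footnote tells sites to watch it. This weighs against the uniform assumption but does not remove the gap.

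A reader might infer from the 4-week and 12-week figures that losses differ between arms and distort the safety comparison. The protocol does not support that. Section 5.8 discontinues study treatment as a whole and lists severe non-compliance as a reason. No passage provides for omitting ZOLADEX while tamoxifen continues, although none excludes it, and no frequency is given.

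**Conclusion.** The point holds as a low-severity inconsistency. Section 6.4.3 uses an incomplete anchor. There is no gap on the planned schedule. With an early last injection inside the permitted window, the stated period closes up to 7 days before tamoxifen ends and before the Week 24 assessment. What falls outside is mainly non-serious AEs. For a given shift the gap is identical in the two arms, so it under-collects without itself biasing the comparison.

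The 7-day maximum rests only on the stated schedule, with the window read around the scheduled weeks. The 1.75-day mean rests on the uniform assumption, and the 4-week and 12-week figures on a missed injection with tamoxifen continued.

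Two stronger readings go too far. One is that on-treatment harms will go uncollected: the text shows only that some fall outside the stated period, and other provisions point to their being recorded. The other is that half of all patients are affected: that figure follows from the uniform assumption alone and counts gaps of any length.

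One limit: the study plan (Table 2) could not be read in the copy used for this check. If it sets an end point for AE recording, that belongs in the same reconciliation.

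**What to change.** Reconcile 6.4.3 with 3.1 so that AE and SAE data collection runs to the latest of (a) the stated interval after the final ZOLADEX injection, (b) the final dose of any study medication, tamoxifen included, and (c) the Week 24/study completion visit. Check the early-discontinuation sentence in 3.1, which has the same ZOLADEX-only anchor, against the new wording, and match the eCRF instructions.

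The cost is about one sentence in each section and a few more AE records. Nothing is added for a patient on the planned schedule, the completion visit already takes place, and no dose or clinical rule changes.
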